#### 11 Treatments

#### 11.1 Treatments administered

Patients will take 50 mg YF476 by mouth once daily for up to 12 weeks. Investigators have the option to increase the dose to 75 or 100 mg *once* daily after 6 weeks' treatment (at Visit 4). If a satisfactory response is seen with 50 mg YF476 *once* daily after 6 weeks for the first few patients, subsequent patients may be started on 25 mg YF476 *once* daily.

For the extended treatment period, patients will receive the same daily dose of YF476 as they did at the end of the initial 12 week period. The investigator will still have the option to increase the patient's dose to 75 or 100 mg once daily, or reduce it to 25 mg, depending on progress.

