#### 9 Overall trial design

Patients will attend the clinic up to 12 times. The time that patients take to complete the trial will depend on their response to YF476.

At Visit 1, patients will be screened (excluding gastroscopy) for eligibility.

At **Visit 2**, patients will undergo gastroscopy and gastric biopsies. If they meet all the inclusion/exclusion criteria, they will start treatment with 50 mg YF476 by mouth *once* daily at home on the next day. Each subject will be given a unique number at the start of treatment.

They will complete a diary card daily throughout the treatment period.

**Visit 3** will be 3 weeks after starting YF476, to assess tolerability, safety and blood levels of gastrin, CgA and YF476.

**Visit 4** will be 6 weeks after starting YF476, to assess tolerability and safety, to repeat the gastroscopy and gastric biopsies, and to take blood samples to assess levels of gastrin, CgA and YF476. If the gastric carcinoids have regressed completely on visual inspection, YF476 will be stopped, Visits 5 and 6 will be omitted, and the patient will proceed to Visit 7. If the gastric carcinoids are still present, YF476 will be continued, but the dose may be increased to 75 or 100 mg *once* daily, at the discretion of the investigator.

**Visit 5** will be 9 weeks after starting YF476, to assess tolerability, safety and blood levels of gastrin, CgA and YF476.

**Visit 6** will be 12 weeks after starting YF476, to assess tolerability and safety, to repeat the gastroscopy and gastric biopsies, and to take blood samples to assess levels of gastrin, CgA and YF476. If the carcinoids have not regressed, the patient will leave the trial. If the carcinoids have regressed, the patients will proceed to Visit 7.

**Visit 7** will be a follow-up visit, 12 weeks after the end of treatment with YF476, only for patients who respond to YF476. The gastroscopy and blood sampling for fasting gastrin and CgA will be repeated.

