# 14.3 Visit 3: 3 weeks after starting YF476

The investigator will:

- check that the patient has fasted;
- collect the diary card, and issue a new one;
- check the diary card for compliance with treatment, and for adverse events and concomitant medication;
- collect YF476 container and assess compliance;
- record a 12-lead ECG, and blood pressure and heart rate;
- collect blood and urine for safety tests, including a pregnancy test for women of child-bearing potential;
- collect blood for assay of fasting levels of gastrin, CgA, YF476 (trough), and serum for storage;
- after taking the fasting blood sample, give the patient their dose of YF476, wait 1 h, and then collect blood for assay of peak concentration of YF476;
- issue a second container of YF476 capsules (25 mg); 2 capsules to be taken with breakfast as before; and
- remind the patient to fast before their gastroscopy on Visit 4.

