# 14.4 Visit 4: 6 weeks after starting YF476

The investigator will:

- check that the patient has fasted;
- collect the diary card, and issue a new one;
- check the diary card for compliance with treatment, and for adverse events and concomitant medication;
- collect YF476 container and assess compliance;
- do a medical examination, including blood pressure and heart rate measurements, and 12-lead ECG;

- collect blood and urine for safety tests, including a pregnancy test for women of child-bearing potential.
- collect blood for assay of fasting levels of gastrin, CgA, YF476 (trough), and serum for storage;
- do a gastroscopy and take gastric biopsies, and proceed as follows:
  - if on visual inspection the gastric carcinoids have regressed completely: stop YF476, omit Visits 5 and 6, and proceed to Visit 7, providing all safety assessments prove satisfactory; or
  - if on visual inspection gastric carcinoids are still present: continue 50 mg YF476 *once* daily or consider increasing the dose to 75 or 100 mg *once* daily, issue a third container of YF476 capsules (25 mg); issue a new diary card;
  - after collecting the fasting blood sample and doing the gastroscopy, give the patient their dose of YF476, wait 1 h, and then collect blood for assay of peak YF476 concentration; and
  - instruct the patient about Visit 5.

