# 20 Trial documentation

# 20.1 Protocol amendments

After the protocol has been approved by the main REC and the MHRA, no changes may be made without the agreement of both the investigator and the sponsor.

The MHRA and main REC do not need to approve any substantial change to the protocol that needs to be implemented urgently to avoid an immediate hazard to trial subjects. The sponsor will ensure that the MHRA and main REC are informed of urgent amendments in accordance with the detailed guidance to EU Directive 2001/20/EC and the standard operating procedures issued by NRES for NHS RECs.

All agreed protocol amendments will be recorded on a written agreement which will be signed and dated by the investigator and sponsor, and attached to the original protocol. The REC and/or MHRA must approve substantial amendments before they are implemented.

The following changes to the trial plan are permitted by this protocol, and will not be considered as amendments.

- (a) Additional visits, for example to monitor blood pressure, will be arranged if there is a potential risk of a drug-drug interaction (see Appendix 1).
- (b) Additional blood or urine samples may be taken for safety tests if required. The total volume of additional blood taken will not exceed 100 mL. Laboratory safety tests will be repeated, if the investigator has any safety concerns.
- (c) Up to 3 additional visits to the clinic will be permitted, in the event of a technical failure and/or it extra safety tests are needed.
- (d) Additional laboratory tests for ECL-cell markers, biomarkers and/or histology will be done on the gastric biopsies, if the results of other tests suggest that additional tests would be worthwhile.
- (e) Stored serum will be used for laboratory tests not yet defined but related to this trial only.
- (f) Visits 3 and 5 may be made up to 2 days before or after the scheduled day. Visits 4, 6 and 7 may be made up to 3 days before or after the scheduled day. Visits 9-12 may be up to 5 days before or after the scheduled day. Patients will be given sufficient YF476 to cover any delays. Therefore, up to 33 days extra YF476 may be taken by each patient, although every effort will be made to arrange patient's visits on the scheduled days.
- (g) It might not be possible to take a video of every gastroscopy. Photographs should suffice.

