- (h) If after the first few patients have completed the trial it is clear that increasing the dose at Visit 4 from 50 mg YF476 *once* daily to 75 or 100 mg *once* daily is necessary for a satisfactory response, and that the regimen is well tolerated, subsequent patients may be started on 75 or 100 mg *once* daily at their next visit.
- (i) If after the first few patients a satisfactory response to the 50 mg YF476 dose once daily is seen at Visit 4, the dose may be reduced to 25 mg YF476 once daily, and subsequent patients may be started on this lower dose.

- (j) Follow-up may be extended if:
  - (i) a subject has an unresolved adverse event, which, in the opinion of the investigator, merits further follow-up; or
  - (ii) new information becomes available that supports an extended follow-up period.

The investigator will decide on the nature of the follow-up. For example, subjects may have a telephone follow-up at which they are asked about adverse events, or subjects may be asked to attend extra outpatient visits for additional monitoring of blood levels or effects of IMP, and for extra safety tests. The extra safety tests might include tests that are not described in this protocol. The investigator reserves the right, during or after the study, to do any extra safety tests that are in the best interest of the subjects. Those extra tests may or may not be described in this protocol.

(k) If the patient has not fasted for Visit 1, fasting safety tests of blood and urine may be done at Visit 2.

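### The permitted starting doses and dose changes are not carried into the visit instructions, and the dosing sections contradict each other

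*Protocol*

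**What the plan says.** **Rules that allow doses other than 50 mg in the initial 12 weeks**

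- Section 11.1 opens with the default, "Patients will take 50 mg YF476 by mouth once daily for up to 12 weeks". It allows an increase to 75 or 100 mg at Visit 4 and then adds that "subsequent patients may be started on 25 mg YF476" once daily. The Summary (Section 2.6) has the same 25 mg option.
- Section 20.1(h) says that, if the first few patients show the higher dose to be needed and well tolerated, "subsequent patients may be started on 75 or 100 mg" once daily, with effect from their next visit.
- Section 20.1(i) says that after a satisfactory response to 50 mg "the dose may be reduced to 25 mg YF476 once daily, and subsequent patients may be started on this lower dose".

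**Text that provides only for a 50 mg start**

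- Section 9, at Visit 2: "they will start treatment with 50 mg YF476 by mouth". It repeats most of Section 2.6 but not the 25 mg sentence.
- Section 11.3 and footnote 3 of Section 6.2 give 50 mg. Section 11.3 foresees only an increase.
- Section 14.2 (Visit 2) issues 25 mg capsules, two a day.
- Section 14.3 (Visit 3): "2 capsules to be taken with breakfast as before".
- Section 14.4 (Visit 4): "if on visual inspection gastric carcinoids are still present: continue 50 mg YF476" once daily, or consider 75 or 100 mg.
- Section 14.5 (Visit 5): two capsules, or three or four if the dose was raised at Visit 4.

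**The concern.** A site doses from the visit instructions. Where the treatment section and the list of permitted changes allow a dose that no instruction from Visit 2 to Visit 5 can issue, the dose a patient is given depends on which section the site follows.

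The rules also disagree among themselves. Section 11.1 says nothing of a 75 or 100 mg start. For the initial 12 weeks it offers no reduction, whereas Section 20.1(i) does. Section 20.1(h) speaks of starting patients at their next visit, which could mean new patients or patients already on treatment.

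Assigned dose matters to the analysis. Section 18.1 (Pharmacokinetic data) plans to examine whether YF476 dose is related to plasma CgA or serum gastrin. Section 11.5 has compliance checked from the diary card and container, which presupposes a clear prescribed count. Section 18.2 looks ahead to a larger trial at a fixed dose. With at most 10 patients, confusion over the assigned dose of one or two would be 10% to 20% of a full trial (1/10 to 2/10).

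**Working it through.** **Inputs**

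- Capsule strength: 25 mg (Section 15.3).
- Starting doses that some part of the protocol permits: 25 mg (2.6, 11.1, 20.1(i)), 50 mg (default), 75 or 100 mg (20.1(h)).
- Capsules a day in the visit text: Visit 2, two; Visit 3, two; Visit 5, two, or three or four after an increase at Visit 4.

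**Dose implied by the visit text** (capsules × 25 mg)

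- Visits 2 and 3: 2 × 25 = 50 mg. This reproduces the protocol's default dose.
- Visit 5: 2 × 25 = 50 mg, 3 × 25 = 75 mg or 4 × 25 = 100 mg.
- One capsule (25 mg) appears in no instruction from Visit 2 to Visit 5.

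**Literal Visit 3 dose against starting dose** (ratio = 50 / starting dose)

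| Starting dose | Capsules needed | Visit 3 text gives | Ratio |
|---|---|---|---|
| 25 mg | 1 | 50 mg | 50/25 = 2.0 |
| 50 mg | 2 | 50 mg | 50/50 = 1.0 |
| 75 mg | 3 | 50 mg | 50/75 = 0.67 |
| 100 mg | 4 | 50 mg | 50/100 = 0.5 |

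**Can each visit deliver each permitted dose?**

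- *Visit 2.* The count is fixed at two with no alternative, so a 25, 75 or 100 mg start already departs from the text here.
- *Visit 3.* The count is again two, but the line also refers back to previous dosing. For a patient not on 50 mg, its two halves disagree.
- *Visit 4.* With carcinoids still present, the options are 50 mg (worded as a continuation), 75 mg or 100 mg. No branch covers a patient on 25 mg, a patient already on 75 or 100 mg who is to stay there, or a reduction.
- *Visit 5.* Three or four capsules depend on an increase at Visit 4. A patient started on 75 or 100 mg and left unchanged at Visit 4 does not meet that condition, so the text gives two.

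**Comparison within the same document.** In the extended period, Visit 8 has the investigator tell the patient how many capsules to take, and Visits 9 and 11 issue capsules to be taken as previously, without a count. That wording works at any assigned dose.

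**The case against.** The best defence is that Section 14 sets out the default plan and Section 20.1 lists the allowed departures. That list is introduced with "The following changes to the trial plan are permitted by this protocol, and will not be considered as amendments", and items (h) and (i) belong to it. Other items work the same way: (g) drops the video and (k) moves fasting tests to Visit 2. A schedule need not restate every permitted exception.

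This has force for 20.1(h) and (i) taken alone. It does not remove the inconsistency. The 25 mg start also stands in Section 11.1, the main treatment section, and is not only a listed exception. Section 11.1 and Section 20.1 differ on which starts and reductions are allowed. Nothing says that the capsule counts at later visits change when an exception is used.

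A reader might go further and infer that the protocol directs a switch to 50 mg at Visit 3 for anyone started on another dose, so that a dosing error is built in. The documents do not support that:

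- Visit 2 fixes the same two capsules. If Section 14 is followed strictly, nobody starts off 50 mg and nobody is switched. A switch at Visit 3 requires the exception to apply at Visit 2 and then lapse.
- The reference back to earlier dosing at Visit 3 can be read as keeping the current dose. The text is ambiguous and does not order a change.
- For 75 and 100 mg, the ratios also assume that 20.1(h) means a start at Visit 2, which its wording leaves open.

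A reader might also infer that the dose actually taken would be lost. That goes too far. Diary cards record each dose, containers are checked at each treatment visit (11.5), dispensing is recorded by subject (15.3.2), and trough and peak YF476 are measured at Visits 3 to 6. Much of the actual exposure could be recovered. The case report form is not shown, so no gap in it can be claimed, and how results are tabulated by dose can be left to the analysis plan.

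**Conclusion.** The point holds as an internal contradiction in the dosing text. Starting doses of 25, 75 and 100 mg are permitted somewhere in the protocol, but none can be delivered by the Visit 2 and 3 instructions as written. Visits 4 and 5 do not provide for patients who started on those doses, and Sections 11.1 and 20.1(h)-(i) do not agree on what is allowed.

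On a literal reading, the Visit 3 count is 2.0, 0.67 or 0.5 times a 25, 75 or 100 mg start. Those ratios assume that a patient did start on the other dose at Visit 2 and that the stated count overrides the reference back to earlier dosing. They measure the discrepancy in the text and do not predict what sites would do.

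The trial has at most 10 patients and makes no power calculation, so no sample-size or error-rate figure is affected. What is affected is the dose issued and the clarity of assigned dose in the planned comparison with CgA and gastrin. The text should be corrected, since the repair is cheap. No view is taken on which dose or dose-change rule is right.

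**What to change.** Reconcile Sections 2.6, 6.2, 9, 11.1, 11.3, 14.2 to 14.5 and 20.1(h)-(i):

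1. State one rule for starting dose and dose change in Section 11.1, and make the other sections repeat it or refer to it. Make clear which patients 20.1(h) and the reduction in 20.1(i) apply to, and from which visit.
2. Have Visits 2 to 5 issue the patient's assigned dose in place of a fixed capsule count, for example with dose-neutral wording like that already used at Visits 8, 9 and 11.
3. Give Visit 4 a branch for every dose that the reconciled rule allows a patient to be on.

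The choice of rule belongs to the sponsor and investigator. The cost is protocol wording, plus whatever approval Section 20.1 requires for the change. It needs no extra visits, samples or patients.

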#### 11.2 Labelling

HMR Pharmacy will label YF476 in accordance with GMP Annex 13. Each subject's treatment will be given a unique code number, traceable to the batch number.

#### **11.3** Selection and timing of dose for each subject

Patients will take 50 mg YF476 by mouth with a glass of water with breakfast. If the dose is increased to 75 or 100 mg, that too will be taken with breakfast. On study visit days, patients will bring their container of YF476 to the clinic to take their dose.

#### **11.4 Previous and concomitant treatment**

Information on co-administered medicines is provided in Appendix 1. The investigator will include information about co-administered medicines in the letter to the patient's general practitioner.

Subjects must record all concomitant treatments in the diary card. Concomitant treatments will be reported in the case report form (CRF) along with their daily dosage, duration and reasons for administration. Subjects who have received any concomitant treatment may be withdrawn from the trial at the discretion of the investigator.

# **11.5** Assessment of compliance

Subjects will record in their diary card the date and time of each dose. At each clinic visit the diary card and YF476 container with be checked for compliance.

# 12 Main outcome measures

### 12.1 Efficacy

Efficacy will be assessed as follows:

- visual assessment of the number, size and distribution of gastric carcinoids at gastroscopy;
- histology and real-time PCR on biopsies for ECL-cell markers and biomarkers (such as CgA); and
- levels of fasting serum gastrin and plasma CgA, and trough and peak plasma YF476.

### 12.2 Safety and tolerability

Vital signs, results of physical examinations, any adverse events (see section 16), laboratory safety variables (see section 14), and ECG variables. Evidence of QTc prolongation will be sought.

# **13** Dietary and lifestyle restrictions

Subjects must make up to 12 visits to the clinic. Before each visit, patients must eat no food for 6 hours and before each gastroscopy visit they must also drink no fluids for 6 hours. They can eat and drink 30 min after gastroscopy.

Subjects must not take certain medicines before, and during, YF476 treatment (see Appendix 1). Pre-menopausal women who are at risk of pregnancy must use one of the recommended methods of contraception for the duration of YF476 dosing (see Section 10.2).

# 14 **Procedures and observations**

# 14.1 Visit 1: Screening for eligibility (part 1)

Patients will be asked to fast for 6 hours before this screening visit. The investigator will complete the following evaluation for each subject and enter the data from this visit, and all subsequent visits, on the appropriate page of the CRF:

- informed consent;
- letter to GP;
- medical history (including evidence for diagnosis of CAG, such as pernicious anaemia, achlorhydria, parietal cell antibody, intrinsic factor antibody, endoscopy and biopsy), medical examination, vital signs (heart rate and blood pressure);
- 12-lead ECG;
- *H. pylori* test (if status unknown);
- fasting serum gastrin, plasma CgA and serum for storage;
- laboratory analyses:
  - haematology: Hb, MCV, haematocrit, WBC and differential, and platelets;
  - biochemistry: urea, creatinine, total bilirubin, total protein, albumin, globulin, alkaline phosphatase, AST, ALT, gamma GT, glucose, cholesterol, triglycerides, potassium, sodium;
  - urinalysis: dipstick test: protein, blood, ketones, glucose, leukocyte esterase, specific gravity, nitrites, pH; microscopy if the result of the dipstick test for protein, blood, leukocyte esterase or nitrites is abnormal; urine pregnancy test only in women of child-bearing potential.

The investigator will tell patients to fast before gastroscopy at Visit 2.

# 14.2 Visit 2: Screening for eligibility (part 2), and start of YF476 treatment

Visit 2 will be within a maximum of 4 weeks after Visit 1. Patients will be asked to fast from food and fluids for 6 hours before this screening visit. The investigator will assess for eligibility all of the patient's results from the first screening visit. Eligible patients will:

- have fasted;
- have a pregnancy test if they are a woman of child bearing potential;
- undergo baseline gastroscopy and gastric biopsies; if the presence of gastric carcinoids is confirmed, the patient will be given the following until the next visit, which will be 3 weeks after Visit 2:

- container of YF476 capsules (25 mg); 2 capsules to be taken with breakfast, starting on the day after gastroscopy; and
- diary card, to record YF476 doses, any adverse events, and any concomitant medication.

It might be possible to combine Visits 1 and 2 for some patients.

The investigator will tell patients to fast before Visit 3, and to bring their container of YF476 capsules with them at the visit.

# 14.3 Visit 3: 3 weeks after starting YF476

The investigator will:

- check that the patient has fasted;
- collect the diary card, and issue a new one;
- check the diary card for compliance with treatment, and for adverse events and concomitant medication;
- collect YF476 container and assess compliance;
- record a 12-lead ECG, and blood pressure and heart rate;
- collect blood and urine for safety tests, including a pregnancy test for women of child-bearing potential;
- collect blood for assay of fasting levels of gastrin, CgA, YF476 (trough), and serum for storage;
- after taking the fasting blood sample, give the patient their dose of YF476, wait 1 h, and then collect blood for assay of peak concentration of YF476;
- issue a second container of YF476 capsules (25 mg); 2 capsules to be taken with breakfast as before; and
- remind the patient to fast before their gastroscopy on Visit 4.

# 14.4 Visit 4: 6 weeks after starting YF476

The investigator will:

- check that the patient has fasted;
- collect the diary card, and issue a new one;
- check the diary card for compliance with treatment, and for adverse events and concomitant medication;
- collect YF476 container and assess compliance;
- do a medical examination, including blood pressure and heart rate measurements, and 12-lead ECG;

- collect blood and urine for safety tests, including a pregnancy test for women of child-bearing potential.
- collect blood for assay of fasting levels of gastrin, CgA, YF476 (trough), and serum for storage;
- do a gastroscopy and take gastric biopsies, and proceed as follows:
  - if on visual inspection the gastric carcinoids have regressed completely: stop YF476, omit Visits 5 and 6, and proceed to Visit 7, providing all safety assessments prove satisfactory; or
  - if on visual inspection gastric carcinoids are still present: continue 50 mg YF476 *once* daily or consider increasing the dose to 75 or 100 mg *once* daily, issue a third container of YF476 capsules (25 mg); issue a new diary card;
  - after collecting the fasting blood sample and doing the gastroscopy, give the patient their dose of YF476, wait 1 h, and then collect blood for assay of peak YF476 concentration; and
  - instruct the patient about Visit 5.

